#### 6.A.2.6. Functional impairment and disability index (BODE index)

The Body mass index, airflow Obstruction, Dyspnoea and Exercise (BODE) capacity index has been shown to predict mortality in patients with COPD. It ranges from 0 to 10 with highest scores indicating higher risks of death.

The BODE index will be calculated for each randomised patient using the following physiological parameters reported by the investigators at Visits 1 and 5 (*see section 6.A.2.5*):

- Forced Expiratory Volume in one second ( $FEV_1$ ), assessed by spirometry and recorded in percentage of predicted values in force in the investigational centre.
- Six-minute walking distance assessed during a six-minute walk test on room air or on oxygen for patients on oxygen therapy and reported in meters.
- Dyspnoea score, assessed by the Modified Medical Research Council (MMRC) dyspnoea scale.
- Weight at each visit and height at Selection, allowing the calculation of the Body Mass Index (BMI).

From these variables, the BODE index will be calculated for each patient at Visits 1 and 5 as follow:

Parameters	Points on BODE Index			
	0	1	2	3
$FEV_1$ (% of predicted values)	$\geq 65$	50–64	36–49	$\leq 35$
6-min walking distance (m)	$\geq 350$	250–349	150–249	$\leq 149$
MMRC dyspnoea scale	0–1	2	3	4
BMI (kg/m  )	$> 21$	$\leq 21$		

**Table 2:** Variables and Point Values Used for the Calculation of the BODE Index

Then, the calculated BODE index will be categorised in 4 quartiles as previously defined : quartile 1 will be defined as a score of 0 to 2, quartile 2 as a score of 3 or 4, quartile 3 as a score of 5 or 6 and quartile 4 as a score of 7 to 10.

#### 6.A.2.7. Anxiety and depression

Anxiety and depression will be assessed for each randomised patient every 6 months (*corresponding to Visits 1, 3 and 5*) using the linguistically validated versions of the Hospital Anxiety and Depression Scale (*HADS provided in Appendix 3*)  for the 4 study countries. The questionnaire consists of seven items for depression (HAD-D) and seven items for anxiety (HAD-A). Each item is scored on a 4-point scale, ranging from 0 to 3. One anxiety and one depression scale are scored by summing patient's answers: a score  $\geq 8$  on either part will be used as the cut-off point for the presence of symptoms suggestive of anxiety or depression. The questionnaire has previously been used to screen depression and anxiety in out-patients with COPD  and patients with COPD requiring oxygen therapy .

#### 6.A.2.8. Compliance to oxygen therapy

Compliance to oxygen therapy will be assessed for each randomised patient being on oxygen therapy at Selection or during his/her study participation using the data stored and downloaded from the *NOWOX* device.

These data will be used to estimate the average daily use of oxygen therapy of each randomised patient being on oxygen therapy during the time period he/she is on oxygen therapy during the *Follow-Up Period*, in hours per day.

Average daily use of oxygen therapy will be calculated from all cumulated percentages of oxygen use per hour recorded by the *NOWOX* device throughout the *Follow-Up Period*, converted to hours and normalised by using the total number of days of the patient's effective follow-up at home (*days during which patient is hospitalised will not be taken into account for the calculation*).

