## **VISITS AT THE INVESTIGATIONAL CENTRE (*VISITS 2 TO 5*)**

**Visits 2 to 5** are scheduled at Month 3, Month 6, Month 9 and Month 12 from Visit 1, respectively. These visits may vary from their planned timelines starting at Visit 1 by  $\pm 30$  days, without modifying the initially planned timelines of the following visits if a given visit needs to be advanced or postponed.

**During Visits 2 to 5**, the investigator will record the following data in the e-CRF:

- Date of Visit,
- Results of the physical examination including vital signs (*i.e.*, *systolic and diastolic blood pressures*), weight and pulse oximetry (*pulse rate and SpO2*) on room air and also on oxygen for patients on oxygen therapy,
- Changes in social conditions, if applicable,
- Changes in smoking status, if applicable,
- Recovery from concomitant diseases since the last visit, if applicable,
- Changes in COPD and non-COPD medication, including oxygen therapy, CPAP, Non-Invasive Ventilation and vaccines (*as detailed in section 5.D*), since the last visit, if applicable,
- Occurrence of COPD exacerbations (*as defined in section 6.A.2.2*) since the last visit,
- Occurrence of other Adverse Events (*see section 6.B*) since the last visit,
- For patients on oxygen therapy, checking of the *NOWOX* device (*to detect the need for an exchange or return of the device at study end*), and, if applicable, the reason for exchanging or returning the *NOWOX* device and the serial number of the new *NOWOX* device assigned, whenever necessary; of note, patients starting oxygen therapy during their study participation will be given a *NOWOX* following the procedure described in section 4.B.3.1 and their start date and criteria for oxygen prescription will be collected, as described in section 4.B.1.2.
- Use of health care services (*see section 6.A.2.3*) since the last visit.

**At Visit 3 (Month 6) and Visit 5 (Month 12 or study end in case of premature withdrawal)**, additional questionnaires and examinations will be performed as follows:

- The SGRQ-C, 15D and HADS questionnaires (*as detailed in sections 6.A.2.4 and 6.A.2.7 and provided in Appendix 3*), self-administered before the consultation with the investigator at **Visit 3 (M6)** and **Visit 5 (M12)**,
- Assessment of the severity of dyspnoea using the modified Medical Research Council Dyspnoea Scale at **Visit 5 (M12)**,
- Comorbidities to allow the calculation of the Charlson Comorbidity Index at **Visit 5 (M12)**,

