#### **5.A.4 Medical devices**

##### 5.A.4.1. NOWOX

[figure not shown]
The medical device *NOWOX* (*Figure 2*) is small (*dimensions are 58 \* 28 \* 60 mm*), light (*total weight of 30 g*), wireless, and maintenance free. It is made of RADEL R and CE-marked.

**Figure 2:** *NOWOX* Device

The *NOWOX* is connected in line between the oxygen source and the patient nasal cannula as shown in Figure 3. The device is compatible with standard nasal cannulae and standard oxygen tubing.

**Figure 3:** *NOWOX* Connection Between the Nasal Cannula and the Oxygen Source

The *NOWOX* is compatible with the following types of oxygen sources:

- Oxygen concentrators,
- Oxygen cylinders (*gaseous oxygen*),
- Stationary and mobile oxygen tanks (*liquid oxygen*).

Of note, *NOWOX* is not to be connected to the oxygen source when the patient is on a CPAP device or a home ventilator.

The device makes measurements every five minutes and stores the summarised data every hour. A data record contains the following fields:

- A unique numeric index to identify the record,
- The GMT date and time of the record,
- The percentage of time during which oxygen flow was detected during the past hour (*in percentage of one hour*),
- The percentage of time of oxygen use during the past hour (*in percentage of one hour*), defined by detection of simultaneous oxygen flow and patient's breathing,
- The average respiration rate recorded during the past hour (*in breaths per minute*),
- The peak respiration rate recorded during the past hour (*in breaths per minute*).

The data stored by the *NOWOX* will be downloaded by the manufacturer when the device is returned by the patient to the investigational centre (*i.e., at the end of the patient's participation in the study, or in case the device has to be replaced for any reason*) using a Personal Computer equipped with a radio frequency communication port and the dedicated software (*NOWOX monitor v1.0*). The data will be identified only with the device serial number, and will be saved on a CD-Rom, which will be sent to LINCOLN, in charge of the study data management. Then, they will be transferred electronically into the trial database (*see section 7.A*).

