In the subgroup of patients on oxygen therapy at Selection and/or during their study participation and on the period of their oxygen prescription overlapping their holding of the *NOWOX* device, the average daily duration prescribed will be tabulated by study group. For each patient for whom a change in the daily duration of oxygen prescription is recorded throughout the *Follow-Up Period*, the individual daily duration of oxygen prescription will be estimated by using the sum of all recorded daily durations prescribed multiplied by the number of days of the corresponding prescription, divided by the total number of days on oxygen therapy. In case of missing or incomplete information necessitating monthly approximation in this average calculation, it will be considered that each month lasts 30.5 days.

**Compliance to oxygen therapy:** in the subgroup of patients on oxygen therapy at Selection and/or during their study participation and on the period of their oxygen prescription overlapping their holding of the *NOWOX* device, the average daily use of oxygen therapy over 24 hours, as well as the average use of oxygen therapy at night (*i.e., over the time interval [22:00 ; 6:00]*) and the average use of oxygen therapy during the day (*i.e., over the time interval [06:00 ; 22:00]*) will be calculated separately over at most eight (8) successive periods (*for the first patients included in the study who have been followed up 24 months*) defined by the scheduled visits of the patients at the investigational centre, without taking into account the recordings collected by the *NOWOX* device on the day of each actual visit, *i.e.,* when applicable, over the successive periods:

- between the day following the actual date of Visit 1 and the day preceding the actual date of Visit 2 (*both included*) (*period 1*),
- between the day following the actual date of Visit 2 and the day preceding the actual date of Visit 3 (*both included*) (*period 2*),
- ... and so on, up to the last period between the day following the actual date of Visit 8 and the day preceding the actual date of Visit 9 (*both included*) (*period 8, if applicable*).

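### Section 6.A.2.8 divides recorded oxygen hours by all at-home follow-up days, which contradicts its own target period and the analysis window in section 7.B.3.5

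*Protocol*

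**What the plan says.** Section 6.A.2.8 covers every randomised patient on oxygen at Selection or at any later point in the study. It names the quantity of interest as average daily use "during the time period he/she is on oxygen therapy during the" Follow-Up Period. The next sentence gives the calculation: recorded use is summed over the whole Follow-Up Period, then "converted to hours and normalised by using the total number of days" of effective at-home follow-up. One exclusion is given: "days during which patient is hospitalised will not be taken into account for the calculation".

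Section 7.B.3.5, under compliance to oxygen therapy, describes the same criterion differently. It works "on the period of their oxygen prescription overlapping their holding of the" device and splits that time by scheduled visits. Visit days are left out ("without taking into account the recordings collected by the" device on those days). Hospital days are not mentioned in that definition.

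On supply, section 4.B.3.2 states under Visits 2 to 5 that "patients starting oxygen therapy during their study participation will be given a" NOWOX device. The flow chart in section 6.E shows dispensing at Visits 1 to 4. A patient prescribed oxygen between visits can therefore be without a device until the next one.

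**The concern.** A patient who begins oxygen part-way through follow-up has at-home days that cannot contribute any recorded use: first the days before the prescription, then any days spent waiting for the device. A patient who stops oxygen has such days at the end. The divisor in section 6.A.2.8, taken as written, keeps all of them. The result is then no longer a measure of compliance with a prescription, because part of the denominator is time when nothing was prescribed or nothing could be measured.

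The second problem is that one named secondary criterion has two definitions. An analyst following section 6 and an analyst following section 7 would report different values for the same patient. The introduction (section 1.C) singles out compliance with long-term oxygen as deserving special attention, so its definition should not depend on which section is read.

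**Working it through.** The protocol states no figure for this criterion, so there is nothing to reproduce. The arithmetic below only illustrates the definitions. Assumptions that are not from the protocol: true use of 15 h/day on every day on oxygen, 365 days of follow-up, no use recorded in hospital, visit days ignored, and the start dates and hospital stay shown.

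Formula: average daily use = (15 × days with recorded use) / (days in the denominator).

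**Case 1: oxygen prescribed on day 122, device given at a visit on day 183, no hospital days.** Recorded days: 365 − 183 = 182.

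| Denominator | Days | Result |
|---|---|---|
| All at-home days (6.A.2.8 divisor as written) | 365 | 15 × 182/365 = 7.5 h/day |
| At-home days since prescription (6.A.2.8 target sentence) | 365 − 122 = 243 | 15 × 182/243 = 11.2 h/day |
| Prescription and device held (7.B.3.5 window) | 182 | 15 × 182/182 = 15.0 h/day |

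The three readings give three values for a patient whose true use is 15 h/day. The middle row shows that applying the target sentence of section 6.A.2.8 removes the days before prescription but not the wait for the device.

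**Case 2: oxygen and device both start on day 90, no wait.** Recorded days: 365 − 90 = 275. The 6.A.2.8 divisor gives 15 × 275/365 = 11.3 h/day; the 7.B.3.5 window gives 15 × 275/275 = 15.0 h/day.

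**Case 3: on oxygen with a device all year, 20 hospital days without recordings.** Recorded days: 365 − 20 = 345. Section 6.A.2.8 removes the hospital days: 15 × 345/345 = 15.0 h/day. If section 7.B.3.5 is read as dividing by days prescribed and held, hospital days stay in: 15 × 345/365 = 14.2 h/day. That reading is conditional, because section 7.B.3.5 does not state a day-count divisor.

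**Unaffected case:** oxygen and device throughout, no hospital stay. Both sections give 15 × 365/365 = 15.0 h/day.

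**The case against.** The strongest reply is that section 6.A.2.8 should be read as a whole. Its target sentence can be taken to govern the divisor, so that effective follow-up at home means at-home days while on oxygen. Section 7.B.1 also points to section 7.B.3.5 for the analysis, and the window there already excludes days without a prescription or a device. On that view section 6 is merely loose, and nothing tabulated or tested is affected.

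Part of this stands. If section 7.B.3.5 is what is run, late starters are not understated. But the charitable reading has to be supplied by the reader: the divisor sentence carries no such limit, and its only exclusion is hospital days. Even so read, it leaves the wait for the device in the denominator (11.2 rather than 15.0 h/day in case 1), and the sections still disagree on hospital days. Deferral to the statistical analysis plan does not settle it. Section 7.B.3.3 leaves missing-data handling to that plan, but section 6.A.2.8 does not defer; it fixes a divisor.

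Four stronger readings are tempting and are not supported:

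- **That section 7.B.3.5 also counts days without prescription or device as non-use.** Its window excludes both.
- **That a failed device counts as non-use in section 7.B.3.5.** This needs a days-held divisor, which the text does not state. It refers to recordings collected, and section 7.B describes parameters by observed case. The absence of a failure rule may be settled in the analysis plan and is not an error by itself.
- **That ventilator and CPAP use invalidates the analysis.** Section 5.A.4.1 says the device "is not to be connected to the oxygen source when the patient is on a CPAP device or a home ventilator", so oxygen delivered then goes unrecorded. But section 7.B.3.5 repeats the analyses on days without such assistance. Which version leads is a matter of preference.
- **That the bias has a known group-level size or differs between arms.** The protocol gives no rate of mid-study starts. Oxygen prescription is at the investigator's discretion (section 5.A.3), both arms have the same visit and dispensing schedule, and oxygen starts are to be tabulated by group.

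**Conclusion.** The divisor in section 6.A.2.8 is wrong as written. It contradicts the sentence before it and the window in section 7.B.3.5, and it turns days without a prescription or a device into zero use. For an individual the effect can be large: 7.5 against 15.0 h/day in case 1, under the assumed 15 h/day and the assumed dates. It is nil for a patient on oxygen with a working device throughout. The effect on group means, or on the comparison of arms, cannot be derived from the protocol. The disagreement on hospital days is a separate, smaller inconsistency.

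The consequence is bounded. Compliance is a secondary criterion, section 7.B declares everything beyond the primary analysis exploratory and descriptive, and the primary criterion is not touched. The point is a conflict of definition to be corrected before analysis.

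**What to change.** Replace the divisor in section 6.A.2.8 and use the same one in section 7.B.3.5: time at home with an active oxygen prescription, the device in the patient's possession and a valid NOWOX record. Average daily use is then 24 × (hours of recorded use) / (eligible hours with a valid record). Hours without a record are missing, not zero. State in both sections that hospital days are excluded, and align the handling of visit days. Report by group the share of at-home prescribed time covered by valid records, so that gaps are visible.

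No new data are needed. Section 5.A.4.1 describes dated hourly records, section 5.D collects start and end dates of oxygen prescriptions, section 6.A.1 collects hospital admission and discharge dates, and device serial numbers are recorded at visits. The order of the analyses with and without CPAP or ventilation days can stay as it is.

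The cost is a wording change in the protocol, carried into the analysis plan. The downside is that patients with long recording gaps contribute less time, and their average rests on the recorded part only; the coverage report lets a reader judge how much that matters.

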#### 6.A.2.9. Smoking status

Smoking status will be reported by the investigators at Visits 0 to 5, as any changes (*e.g., stopping or re-starting smoking*) may impact the outcome measurements. Results of HbCO measurements performed from the arterial or capillary blood gas sample at Visits 1 and 5 will also be considered.

## 6.B SAFETY EVALUATIONS

All Adverse Events (AEs) occurring during the whole study period will be recorded as detailed in section 8. Their reports in the e-CRF will include:

- The nature of the events, their start and end dates, their severity,
- The corrective treatment(s) started if applicable,
- The required adjustment of COPD medication, including oxygen therapy, home ventilation, if applicable,
- The outcome of the events and their relationship to the allocated study intervention as assessed by the investigator.

AEs will include all hospitalisations, whatever their associated diagnoses afterwards, and deaths throughout the study period.

### **6.B.1 Clinical parameters**

A physical examination including vital signs (*i.e.*, systolic and diastolic blood pressures), weight and pulse oximetry (*for the measurement of pulse rate and SpO2*) on room air and also on oxygen for patients on oxygen therapy will be recorded at each of the **six (6)** visits at the investigational centre.

A 12-lead supine resting electrocardiogram (ECG) will be performed prior to Visits 1 and 5 and potential significant abnormalities will be recorded by the investigators in the e-CRF.

The Charlson Comorbidity Index will be used to assess the importance of comorbidities. It will be calculated by the e-CRF for each randomised patient based on the comorbidities reported by the investigator at Visits 1 and 5. The Charlson Index contains 19 conditions. Each comorbid condition is assigned to a score of 1 to 6, proportional to the disease-related risk of death. Myocardial infarction, congestive heart failure, peripheral vascular disease, cerebrovascular disease, dementia, COPD, connective tissue disease, peptic ulcer disease, mild liver disease and diabetes are assigned a score of 1. A score of 2 is assigned to diabetes with end-organ damage, hemiplegia, renal disease and malignancies, including leukaemia and lymphoma. A score of 3 is assigned to moderate or severe liver disease, whereas AIDS and metastatic malignancies are assigned a score of 6. The global score ranges from 0 to 33, the highest scores indicating more comorbidities, and it was shown to be predictive of mortality in COPD.

### **6.B.2 Laboratory parameters**

Prior to Visits 1 and 5, the following blood samples will be assayed by the laboratory of each investigational centre for each randomised patient:

- Resting arterial or capillary blood gases on room air, *i.e.*, pH, PaO2, PaCO2, HCO3, HbCO and SaO2.
- Venous blood sampling: haemoglobin (*anaemia will be defined as a haemoglobin level below 13 g/dL and polycythemia as a haemoglobin level ≥ 17g/dL for males and ≥ 15g/dL for females*), haematocrit and CRP.

Additional blood samples may be collected at the investigator's discretion, in the patient's interest, in case of technical problems during the initial assays performed and/or clinically significant abnormalities evidenced requiring specific additional checks and follow-up until stabilisation or normalisation.

## **6.C MEDICO-ECONOMIC EVALUATIONS**

### **6.C.1 Costs estimation**

Overall costs will be estimated for each randomised patient from the perspective of the health care payer (*i.e.*, the National Health System in force in the country, with the latest version of the corresponding national tariffs system and reimbursement schedule available at the end of the study). The unit will be the patient. Only health care direct costs will be considered, neither the costs to the family nor the costs to the society will be estimated.

Overall resources used for the patient's medical management (*collected in volume, i.e., by type and/or unit of time, before being priced according to the national tariffs system in force*) will be recorded prospectively alongside the study by the study personnel, as the data used to estimate the overall costs from the perspective of the health care payer for each randomised patient have four (4) components which are part of the clinical parameters recorded, including:

- For each unscheduled hospitalisation (*including home hospitalisations*): the dates of admission and discharge, the type of facility, the primary and secondary diagnoses (*as mentioned in section 6.A.1*), as well as the additional expensive medical procedures and acts performed during hospitalisation, if relevant (*including laboratory and other diagnosis examinations*), and the specific expensive treatments administered or technical devices and equipments used during hospitalisation, whenever possible,
- For each health care consultation: the date, the location, the category of health care provider consulted and the reason for consulting (*as detailed in section 6.A.2.3*),
- For the patients in the Intervention group and for each unscheduled phone call to the health counsellor (*on patient's request or because of symptom scoring*): the date, the reason for calling, as well as the duration of the phone call and associated procedures set up by the health counsellor, and duration of the investigator actions in case of confirmed alarm status (*as mentioned in section 6.A.2.3*),
- For the patients in the Intervention group and for each scheduled education session: the date and duration of the education session performed, its type and location.

